#### 8.5 SEARCH FOR INFECTIONS

Search for infections that represent exclusion criteria include the following pathogens:

- *Mycobacterium Tuberculosis*

At screening, it will be performed via IFN $\gamma$ -release assay or PPD test. In addition, a baseline via polymerase chain reaction [PCR] in a relevant specimen (e.g., urine or blood, if sputum is not easily obtained) has to be obtained, as this test will be used during the course of the study to perform regular TB monitoring.

After initiation of emapalumab treatment, search for TB via PCR has to be performed every 2 weeks as long as emapalumab is detectable in serum.

In the case of a patient having received BCG vaccination, a PPD test must be performed and combined with an IFN $\gamma$ -release assay.

- *Atypical mycobacteria, Shigella, Salmonella, Campylobacter, Histoplasma Capsulatum and Leishmania*

Search for all these pathogens have to be performed at screening. During the study, search for these pathogens has to be performed if there is any suspicion of infection.

A first screening for *Histoplasma Capsulatum* may be performed using galactomannan assay, however if the test is positive, confirmation should be obtained by using a *Histoplasma Capsulatum* specific test. The presence of *Leishmania* can be ascertained by direct bone marrow observation.

In addition, search for the following infections is required:

- *Herpes Simplex Virus (HSV), Herpes Zoster Virus (HZV), Hepatitis B Virus (HBV), Hepatitis C Virus (HCV), Human Immune Deficiency Virus (HIV)* by PCR monitoring or serology, at screening and whenever there is a suspicion of infection.
- *EBV, CMV, Adenoviruses* by quantitative PCR, at screening and every 2 weeks as long as emapalumab is detectable in serum.

A patient with a clinical assessment (including chest X-ray) not indicative of the presence of an active infection, provided that a usable specimen has been taken and the microbiological analysis is ongoing, can be enrolled prior to the availability of the results, if the patient's clinical conditions require a rapid initiation of emapalumab treatment.

## 8.6 IMAGING

### 8.6.1 Abdominal ultrasound

Abdominal ultrasounds, including spleen (longitudinal) measurements and assessment of hepatomegaly presence, will be performed at screening and every 2 weeks during the study.

### 8.6.2 Chest X-ray

Chest X-ray will be performed as a measure for detection of pulmonary infections at screening and every 4 weeks during the study. Chest X-ray should be done more frequently in case of clinical suspicion of a pulmonary infection.

### 8.6.3 Brain MRI

Brain MRI should be performed in case of neurological symptoms occurrence, prior to emapalumab initiation (or at latest by SD6), and repeated at the end of the study, whenever possible.

## 8.7 OTHER PROCEDURES

### 8.7.1 ECG

12-lead ECG will be performed and interpreted locally by the Investigator or delegate for immediate clinical assessment.

At screening, triplicate ECG (three consecutive recordings) is required in order to obtain a stable baseline.

ECG is mandatory at screening, after the first emapalumab infusion, and at the end of the study, however it should also be performed whenever required based on clinical judgment.

### 8.7.2 Cerebrospinal fluid assessment

Lumbar puncture for CSF analysis should be done in case of neurological symptoms occurrence, whenever possible and if coagulation parameters allow, prior to emapalumab initiation, during the course of the study and at the end of the study, as clinically indicated.

## 8.8 PHARMACOKINETIC/PHARMACODYNAMIC ASSESSMENTS

### 8.8.1 Pharmacokinetics

Serum samples for PK analysis will be collected at the visits indicated in the SoA (Table 1 and Table 2). In case of need for prioritization of blood analysis (considering weight and health status of the patient), laboratory safety parameters (which would be done as normal disease monitoring) may need to be prioritized over samples for PK assessments, that in turn will be prioritized over biomarkers exploratory parameters.

On the days of infusion, PK samples should be collected before and after (between 15 and 30 minutes after) the infusion.

After the first emapalumab infusion, PK samples will be also collected on SD1 (around 24 hrs. post-infusion) and SD2 (around 48 hrs. post-infusion). Additionally, PK samples will be collected on SD5 (around 48 hrs. after the second emapalumab infusion).

After completion of emapalumab infusions, samples for PK assessment will be collected until serum emapalumab concentration are no longer detectable (or until consent is withdrawn), as indicated in the SoA until the EoS visit. In case of CNS involvement, if lumbar puncture is performed for diagnostic and/or therapeutic purposes, PK analysis in CSF samples may be performed.

Details on sample preparation and handling will be described in a separate laboratory manual.

### 8.8.2 Pharmacodynamics

Serum samples for PD analysis will be collected at the visits indicated in the SoA (Table 1 and Table 2). In case of need for prioritization of blood analysis (considering weight and health status of the patient), laboratory safety parameters and PK assessments will be prioritized over biomarkers exploratory parameters.

Pharmacodynamics assessments include the measurement of:

- Free IFN $\gamma$  levels prior to emapalumab treatment start, and total IFN $\gamma$  (free IFN $\gamma$ +bound to emapalumab) during emapalumab treatment. Samples for total IFN $\gamma$  measurements will be taken pre-dose on infusion visits, except for the first infusion when free IFN $\gamma$  will be measured pre-dose and total IFN $\gamma$  post-dose.
- Chemokines known to be induced by IFN $\gamma$  (CXCL9, CXCL10) and sCD25. On infusion visits, serum samples will be collected pre-dose only.
- Other potential disease markers (e.g., sCD163, IL-18, IL-10, IL-6, TNF $\alpha$ ). Serum samples will be collected on SD0 and every 2 weeks during the course of the study.

In case of CNS involvement, if lumbar puncture is performed for diagnostic and/or therapeutic purposes, biomarker analysis in CSF samples may be performed.

Details on sample preparation and handling will be described in a separate laboratory manual.

### 8.8.3 Immunogenicity

Serum samples for the assessment of ADAs will be collected on SD0 (prior to emapalumab infusion) and at the End of Study visit, and in case of PK Clearance of emapalumab is faster than expected during the study. Details on sample preparation and handling will be described in a separate laboratory manual.

### 8.9 WITHDRAWAL VISIT

The same procedures described for the EoS Visit should be followed by the Investigator for any patient who is withdrawn prematurely from the study, as soon as possible after the decision to withdraw is made.

For patients who withdraw from the study as a result of their own decision or the decision of their parent/guardian, the Investigator should contact the patient (or parent/guardian) and ask them to attend a withdrawal visit as soon as possible and in any case within 30 days from termination.

Patients who are withdrawn due to a serious adverse event (SAE) should be followed-up until the resolution of the event or until the outcome of the event is known and stable.

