### 3.4 FOLLOW-UP PERIOD

All patients who have received at least one dose of emapalumab will be monitored after the last administration of emapalumab. A short-term follow-up of at least 4 weeks has to be performed under the current protocol, therefore should emapalumab treatment in a given patient need to be prolonged beyond 4 weeks, additional visits will be performed weekly until completion of the 4-week short-term follow-up.

The last visit for a given patient under the NI-0501-06 study will normally be on SD56 (except in case of prolongation of emapalumab treatment beyond 4 weeks, as above described).

Afterwards all patients will be asked to enter a long-term follow-up study, NI0501-05, to allow long-term outcome and safety surveillance, and to monitor emapalumab elimination profile.

In the event that additional monitoring of emapalumab concentrations is required (e.g., emapalumab serum levels still measurable at EoS) and cannot be performed in the context of the long-term follow-up study, unscheduled visits will have to be performed beyond SD56, until serum emapalumab levels are no longer detectable. These measurements should occur not less than every two weeks.

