## 6.5 RESCUE THERAPY

Patients who are withdrawn from the study due to a safety issue or for lack of efficacy (i.e. worsening of MAS/no response to emapalumab) will be treated according to the standard of care at the site.

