**Table 2 – Schedule of assessment: Evaluation period - from SD28 to SD56 (End of Study)**

Assessments			SD35 1 st Week Follow-up	SD42 2 nd Week Follow-up	SD49 3 rd Week Follow-up	SD56  4 th Week Follow-up – EoS 	Unscheduled Visit (UV) 
Hospitalization		8.1					
Concomitant medication (including information on glucocorticoid tapering)		8.2	X	X	X	X	
Clinical assessments	- Vital signs	8.3.1	X	X	X	X	X
	- Physical examination	8.3.2	X	X	X	X	X
	- MAS clinical signs and symptoms 	8.3.3	X	X	X	X	
Laboratory assessments	- CBC	8.4	X	X	X	X	
	- Lymphocyte subset	8.4				X	
	- Coagulation (aPTT, PT, D-Dimers, Fibrinogen)	8.4	X	X	X	X	
	- Biochemistry	8.4	X	X	X	X	
	- Serum pregnancy test	8.4				X	
	- Urinalysis	8.4				X	
Search for infections	- Mycobacterium Tuberculosis	8.5		X		X	
	- EBV, CMV, Adenoviruses	8.5		X		X	
Procedure	- ECG	8.7.1				X	
Imaging	- Abdominal US	8.6.1		X		X	
	- Chest X-ray	8.6.2				X	
	- Brain MRI 	8.6.3				X	
Histopathology	- CSF analysis (if coagulation allows) 	8.7.2				X	
PK	- emapalumab serum concentration	8.8.1	X	X	X	X	
PD 1	- IFN $\gamma$ , CXCL9, CXCL10, sCD25	8.8.2	X	X	X	X	
PD 2	- Other markers	8.8.2		X		X	
Immunogenicity (ADA)		8.8.3				X	

 If Emapalumab treatment needs to be prolonged beyond 4 weeks, additional weekly visits must be scheduled as appropriate in order to complete the required short-term 4-week follow-up.

 The same procedures described for End of Study Visit should be followed for any patient who is withdrawn prematurely from the study (see protocol [Section 8.9](#))

 Unscheduled Visit: depending on the reason for UV, additional assessments may be added according to the Investigator's clinical judgment (see protocol [Section 8.10](#)).

 Hospitalization: please note that the patients can be discharged from SD15 if their conditions allow, provided that there is no active infections requiring i.v. antimicrobial therapy.

 Brain MRI & CSF analysis: to be performed in case of neurological symptoms occurrence, whenever possible. If brain MRI and CSF analysis were done at screening, an End of Study exam should be performed, whenever possible.

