## 10.3 RECORDING AND REPORTING SAFETY PARAMETERS

### 10.3.1 Adverse events

Adverse events (AEs) are defined as any undesirable experience occurring to a subject during the study, whether or not considered related to the IMP. All AEs reported by the patients or his/her relatives or observed by the Investigator or his staff during the clinical study from the signature of the ICF up to and including the EoS visit will be reported on the AE data collection form.

Medical conditions present at screening (before ICF signature) should be recorded in the medical history section of the CRF.

All AEs will be reported in the appropriate section of the CRF.

An AE which occurs between start of screening visit (after ICF signature) and start of first IMP administration will be considered as a pre-treatment AE.

Any AE that occurs after the start of the first IMP administration will be considered in the study as Treatment Emergent Adverse Event (TEAE).

However, if a pre-existing medical condition recorded in the medical history worsens (clinically significant change in intensity or frequency), it must be recorded as an AE in the CRF and, depending on the time of its occurrence, will be considered as a pre-treatment AE or a TEAE. If a medical condition, recorded as a pre-treatment AE, worsens it will be recorded in the CRF as a separate TEAE.

For each AE, the following will be assessed and recorded: intensity, relationship to the IMP, action taken regarding the IMP, any treatment received for the event and outcome of AE to date.

Intensity of AEs will be graded on a three-points scale (mild, moderate, severe) using the modified WHO (World Health Organization) toxicity scale (Grade 3 and 4 are considered to be the severe grade). If AE severity cannot be assessed by this scale, assessment by the Investigator should be made using the following definitions:

- Mild: discomfort noticed but no disruption of normal activity,
- Moderate: discomfort sufficient to reduce or affect normal daily activity,
- Severe: inability to work or perform normal daily activity.

For a given AE, the assessment of its intensity should reflect the highest grade (on the 3 points scale mentioned above) reported during its course (except when the intensity of a pre-treatment AE increases after treatment initiation, as indicated above).

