### **12.1 SAMPLE SIZE**

Approximately 12 patients (a minimum of 10 sJIA patients) will be enrolled across North America and Europe. The sample size is based on pragmatic considerations, and on the experience acquired from primary HLH patients treated with emapalumab.

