### 12.3.5 Missing Data

No imputations of missing data will be performed. However, the following rules will be applied to ensure that all patients can be included in the final analysis:

- patients who are withdrawn from the study prior to Week 8 because of safety concerns or poor efficacy will be classified as non-responders from the time of their withdrawal in all

analyses of response status, and their data will be censored at time of withdrawal in all time-to-event analyses. For continuous endpoints in such patients, all analyses for time points beyond the point of withdrawal will exclude missing data for these patients.

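### For patients withdrawn within 4 weeks of their last infusion, the protocol does not reconcile early End of Study procedures with the mandatory 4-week follow-up, and its survival censoring rule conflicts with the SAP

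*Protocol*

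**What the plan says.** All references are to the current (emapalumab) protocol and to the SAP.

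- **Follow-up.** Protocol 3.4 covers everyone who received at least one dose: "A short-term follow-up of at least 4 weeks has to be performed under the current protocol". It makes no exception for withdrawn patients.
- **Withdrawal visit.** Protocol 8.9 applies the EoS procedures "for any patient who is withdrawn prematurely from the study, as soon as possible after the decision to withdraw is made". Where the patient or parent decides to leave, the site asks for a "withdrawal visit as soon as possible and in any case within 30 days from termination". Table 2 footnote 2 agrees: "The same procedures described for End of Study Visit should be followed for any patient who is withdrawn prematurely from the study".
- **AE window.** Protocol 10.3.1 runs AE reporting from consent "up to and including the EoS visit".
- **Who counts as withdrawn.** Protocol 6.5 refers to "Patients who are withdrawn from the study due to a safety issue or for lack of efficacy". Protocol 11.1.2 covers the same two reasons but speaks only of discontinuing study treatment.
- **Censoring.** For patients withdrawn before Week 8 for safety or poor efficacy, protocol 12.3.5 says "their data will be censored at time of withdrawal in all time-to-event analyses". SAP 6.1.7 measures survival to the date of death and censors survivors at last contact, or at consent withdrawal. SAP 11 does not mention the difference and states that no further changes from the protocol analyses are planned.

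**The concern.** Patients who stop early because of remission keep the visit schedule: to SD28 under protocol 3.3 and 8.1, and to SD56 under SAP 3.1. No matching sentence protects patients who leave because the drug failed or harmed them. Those patients move to site standard of care while antibody is probably still circulating, and protocol 10.5.2.2 itself associates profound immune suppression with a higher infection risk. If their AE window closes at the withdrawal visit, safety follow-up is shortest where risk is likely to be highest.

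Censoring survival at withdrawal for failure is informative, because the reason for leaving is related to the risk of death. Both problems push the infection and survival summaries in the drug's favour. The study is small ("The sample size is based on pragmatic considerations", about 12 patients), so each event carries weight. Protocol 1.2.1 cites MAS mortality reaching 20–30%.

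**Working it through.** **1. Normal case.** Last infusion SD28 + 28 days = SD56, which is the last visit given in protocol 3.4. The plan is consistent for patients who complete it.

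**2. Withdrawn case.** Post-dose days not covered = 28 − (days from last infusion to withdrawal visit), if AE collection ends at that visit. The visit days are assumptions; 3 to 4 days corresponds to withdrawal when the next infusion is due.

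| Visit, days after last infusion | Days uncovered | Share of 28 |
|---|---|---|
| 0 | 28 | 100% |
| 3 | 25 | 89% |
| 4 | 24 | 86% |
| 7 | 21 | 75% |
| 14 | 14 | 50% |

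**3. Is drug still present?** Fraction remaining = 0.5^(days / half-life), single exponential. Protocol 1.1.3 gives about 22 days in healthy volunteers. Protocol 5.3 expects faster clearance when IFNγ production is high, so half-lives of 3 to 14 days are assumed as a range.

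- 22 days: 91% at day 3, 88% at day 4, 41% at day 28.
- 3 to 14 days: 40% to 86% at days 3–4, 0.2% to 25% at day 28.

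Worked example, withdrawal on SD10 after 6 mg/kg on SD0 and 3 mg/kg on SD3, SD6 and SD9 (15 mg/kg given):

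- Half-life 22: 6·2^(−10/22) + 3·[2^(−7/22) + 2^(−4/22) + 2^(−1/22)] = 12.3 mg/kg, or 12.3/15 = 82%. After a further 28 days, 12.3·2^(−28/22) = 5.1 mg/kg.
- Half-life 7 (assumed): the same sum gives 8.47 mg/kg, or 8.47/15 = 56%. After a further 28 days, 8.47·2^(−28/7) = 0.53 mg/kg.

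**4. What the other provisions cover.**

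- Protocol 3.5, 8.9 and 10.4.1 follow events that already exist.
- Protocol 8.5 continues searches for TB, EBV, CMV and adenoviruses every 2 weeks while drug is detectable. Section 10.5.2.3 continues monitoring for infections favoured by IFNγ neutralisation.
- Protocol 3.6 invites dosed patients into a separate, voluntary long-term study.

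None of these requires reporting of other new AEs, or of a death, after the withdrawal visit.

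**5. Survival.** Assume 2 of 12 patients are withdrawn for failure on SD10, both die before SD56, and nobody else dies or is lost.

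- Protocol 12.3.5: both are censored on SD10, no deaths are counted, and the Kaplan–Meier estimate is 100%.
- SAP 6.1.7 with both deaths recorded: 10/12 = 83%.
- SAP 6.1.7 with vital status not collected after withdrawal: last contact may be the withdrawal visit, and the estimate is again 100%.

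**6. Weight of one event.** 1/12 = 8.3 percentage points. The exact 95% interval is 0–26.5% for 0/12 and 0.2–38.5% for 1/12.

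**The case against.** The best defence is that no sentence says the withdrawal visit ends AE collection. Section 8.9 borrows the EoS procedures, whereas the EoS visit in Table 2 is the SD56 column. Section 3.4 is unconditional, so a site could do the withdrawal assessments and still complete 4 weeks of follow-up. Section 11.1.2 stops treatment only, and 10.4.2 likewise distinguishes stopping the drug from leaving the study. Section 10.3.2 requires SAE reporting throughout the study. When drug is still measurable at EoS, 3.4 provides for further visits. On censoring, protocol 12 calls itself an overview, and the SAP survival definition does not contain the rule.

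Much of this stands. AE closure is an inference, though the natural one, because no later end date for new events is given for a withdrawn patient. Own-decision withdrawals have up to 30 days for the visit, and follow-up cannot be enforced after consent is withdrawn. The extra visits in 3.4 are for drug concentrations and are worded as falling after SD56. Section 10.3.2 does not say whether it reaches a patient who has left.

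A reader might infer that infections and deaths in these patients will certainly be lost, that nearly all the drug is still on board, or that the data monitoring committee cannot see later deaths. The documents do not support any of these. Several monitoring provisions continue, the worked example leaves 56% to 82% of the dose given, and nothing prevents a site from reporting a death.

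**Conclusion.** The concern holds as an unreconciled conflict with a possible, not certain, loss of data. For a patient withdrawn from the study within 4 weeks of the last infusion, 3.4 cannot be squared with 8.9 and Table 2 footnote 2 read together with 10.3.1. Sections 6.5 and 11.1.2 leave it unclear which patients are affected. On the natural reading, up to 28 of the 28 required days go uncovered for new AEs and deaths, and 24 to 25 if the visit falls when the next infusion is due.

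The survival conflict is firmer, because two written rules disagree and SAP 11 does not record it. Its effect depends on which rule is applied and on whether vital status is collected. The 100% against 83% contrast is an illustration with assumed deaths, not a forecast: a reader should not infer that the SAP as written would censor these patients at withdrawal. All endpoints are exploratory and descriptive, so no test is affected. What is exposed is the credibility of the infection and survival summaries in about 12 patients.

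**What to change.** 1. Reconcile protocol 3.4, 6.5, 8.9, 10.3.1, 11.1.2 and Table 2 footnote 2 by defining treatment discontinuation and study withdrawal as separate events.
2. State that AE, SAE and vital-status collection runs to at least 4 weeks after the last infusion, with vital status also recorded at SD56, for every treated patient unless consent is withdrawn. Put the EoS procedures at the end of that period.
3. In protocol 12.3.5, exempt survival from censoring at withdrawal so that SAP 6.1.7 governs, and record the change in SAP 11.

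The cost is a protocol amendment, a line in the SAP, and a few visits or calls in a few patients. The infection and survival figures may come out less favourable. When and why treatment is stopped need not change; only data collection and analysis do.

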### 8.10 UNPLANNED (UNSCHEDULED) VISITS

Unplanned visits may occur, should the patient need to be assessed or treated for any clinical condition that arises during the study. This may include the evaluation and follow-up of AEs, SAEs or laboratory tests. The assessments (as detailed in the SoA) should always be performed *at minimum*, but additional evaluations may be added according to the clinical judgment of the Investigator.

#### 8.10.1 Unplanned Assessments

Additional samples to assess laboratory parameters and PK/PD may be required for safety reasons and/or for a better characterization of the PK/PD profile.

The number of additional samples taken will depend on the body weight and health status of the patient. Sampling schedule will be proposed by the Sponsor and discussed with the Investigator.

## 9 STUDY SCIENTIFIC OVERSIGHT

A Scientific Steering Committee (SSC) composed of international experts in pediatric rheumatology as well as in HLH has been involved in the preparation of study design and protocol writing.

The SSC is also to be consulted for the composition of the independent Data Monitoring Committee (iDMC).

The SSC will continue to play an advisory role throughout the course of the study, including the support to the iDMC oversight, and will perform evaluations of the data to support the Sponsor in the interpretation of the results of the study.

Please refer to [Appendix C](#) for full details of membership of the SSC.

